## **Appendix B: Imputation Rules for Missing Prior/Concomitant Medication Dates**

Imputation rules for missing or partial medication start/stop dates are defined below:

- 1. Missing or partial medication start date:
  - a. If only DAY is missing, use the first day of the month.
  - b. If DAY and Month are both missing, use the first day of the year.
  - c. If DAY, Month and Year are all missing, use a date before the first dose date.
- 2. Missing or partial medication stop date:
  - a. If only DAY is missing, use the last day of the month.
  - b. If DAY and Month are both missing, use the last day of the year.
  - c. If DAY, Month and year are all missing, assign 'continuing' status to stop date.

In summary, the prior, concomitant or post categorization of a medication is described below.

Table 11-4 Prior, Concomitant, and Post Categorization of a Medication

	Medication Stop Date				
Medication Start Date	< First Dose Date of Study Drug	≥ First Dose Date and ≤ End Date of TE Period	> End Date of TE Period		
< First dose date of study drug	P	PC	PCA		
≥ First dose date and ≤ End date of TE period	-	С	CA		
> End date of TE period	=	-	A		

A: Post; C: Concomitant; P: Prior

## **Appendix C: Imputation Rules for Missing AE dates**

Imputation rules for missing or partial AE start date are defined below:

#### If only Day of AE start date is missing:

If the AE start year and month are the same as that for the first dose date, then:

- If the full (or partial) AE end date is NOT before the first dose date or AE end date is missing, then impute the AE start day as the day of first dose date; otherwise, impute the AE start day as 1.
- Otherwise, impute the AE start day as 1.

Compare the imputed AE start date with TE period to determine whether the AE is pretreatment AE, TEAE or post-treatment AE.

## If Day and Month of AE start date are missing:

If AE start year = first dose year, then:

- If the full (or partial) AE end date is NOT before the first dose date or AE end date is missing, then impute the AE start Month and Day as the Month and Day of first dose date; otherwise, impute the AE start Month as January and the Day as 1.
- Otherwise, impute the AE start MONTH as January and the DAY as 1.

Compare the imputed AE start date with TE period to determine whether the AE is pretreatment AE, TEAE or post-treatment AE.

#### If Year of AE start date is missing:

If the year of AE start is missing or AE start date is completely missing then query site with no imputation. Also compare the full (or partial) AE end date to the first dose date. If the AE end date is before the first dose date then the AE should be considered as a pretreatment AE. Otherwise, the AE will be considered as TEAE.

# Appendix D: Analysis Visit Window Mapping Rules for Safety and Efficacy Assessments

**Table 11-4 Analysis Visit Windows for Safety Assessments for Part B** 

Safety Assessment	Visit a	Target Study Day	Analysis Visit Window (in study days)
Serum Chemistry	Baseline	1	≤1
	Week 2	14	[2,35]
	Week 8	56	[36,70]
	Week 12	84	[71,105]
	Week 18	126	[106,147]
	Week 24	168	[148, Date of Week 24 Visit]
	Follow-up Visit	NA	Use nominal visit
LFTs	Baseline	1	≤1
	Week 2	14	[2,21]
	Week 4	28	[22,42]
	Week 8	56	[43,70]
	Week 12	84	[71,105]
	Week 18	126	[106,147]
	Week 24	168	[148, Date of Week 24 Visit]
	Follow-up Visit	NA	Use nominal visit
Hematology	Baseline	1	≤1
	Week 4	28	[2,42]
	Week 8	56	[43,70]
	Week 12	84	[71,105]
	Week 18	126	[106,147]
	Week 24	168	[148, Date of Week 24 Visit]
	Follow-up Visit	NA	Use nominal visit
Standard 12-Lead ECG	Baseline	1	≤1
	Week 4	28	[2,56]
	Week 12	84	[57,126]
	Week 24	168	[127, Date of Week 24 Visit]
Vital Signs	Baseline	1	≤1

	Week 2	14	[2,21]
	Week 4	28	[22,42]
	Week 8	56	[43,70]
	Week 12	84	[71,105]
	Week 18	126	[106,147]
	Week 24	168	[148, Date of Week 24 Visit]
	Follow-up Visit	NA	Use nominal visit
Ophthalmologic Exam	Baseline	1	≤1
	Week 12	84	[2,126]
	Week 24	168	[127, Date of Week 24 Visit]
	Follow-up OE visit	NA	Use nominal visit

When a subject is lost to follow up and last dose date is unknown, impute last dose date of all study drugs as last on-treatment visit date.

<sup>aVisit name is used to report data in tables, listings and figures.

Table 11-5 Analysis Visit Windows for Efficacy Assessments for Part B

Safety Assessment	Visit a	Target Study Day	Analysis Visit Window (in study days)
	Follow-up Visit	NA	Use nominal visit
weat Chloride	Baseline	1	≤1
	Week 2	14	[2,49]
	Week 12	84	[50,126]
	Week 24	168	[127, Date of Week 24 Visit]

When a subject is lost to follow up and last dose date is unknown, impute last dose date of all study drugs as last on-treatment visit date.

aVisit name is used to report data in tables, listings and figures.

Table 11-6 Analysis Visit Windows for Safety Assessments for Part A/B Cohort 8

Safety Assessment	Visit a	Target Study Day	Analysis Visit Window (in study days)	
Serum Chemistry	Baseline	1	≤1	
	Day 4	4	[2,9]	
	Day 15	15	[10,21]	
	Week 4	28	[22,42]	
	Week 8	56	[43,70]	
	Week 12	84	[71,105]	
	Week 18	126	[106,147]	
	Week 24	168	[148, Date of Week 24 Visit]	
	Follow-up Visit	NA	Use nominal visit	
Hematology	Baseline	1	≤1	
	Day 15	15	[2,21]	
	Week 4	28	[22,56]	
	Week 12	84	[57,105]	
	Week 18	126	[106,147]	
	Week 24	168	[148, Date of Week 24 Visit]	
	Follow-up Visit	NA	Use nominal visit	
Standard 12-Lead ECG	Baseline	1	≤1	
	Day4	4	[2,16]	
	Week 4	28	[17,56]	
	Week 12	84	[57,105]	
	Week 18	126	[106,147]	
	Week 24	168	[148, Date of Week 24 Visit]	
Vital Signs	Baseline	1	≤1	
	Day 4	4	[2,9]	
	Day 15	15	[10,21]	
	Week 4	28	[22,42]	
	Week 8	56	[43,70]	
	Week 12	84	[71,105]	
	Week 18	126	[106,147]	

	Week 24	168	[148, Date of Week 24 Visit]
	Follow-up Visit	NA	Use nominal visit
Ophthalmologic Exam	Baseline	1	≤1
	Week 12	84	[2,126]
	Week 24	168	[127, Date of Week 24 Visit]
	Follow-up OE visit	NA	Use nominal visit

When a subject is lost to follow up and last dose date is unknown, impute last dose date of all study drugs as last on-treatment visit date.

Table 12-7 Analysis Visit Windows for Efficacy Assessments for Part A/B Cohort 8

Safety Assessment	Visit a	Target Study Day	Analysis Visit Window (in study days)
Sweat Chloride	Baseline	1	≤1
	Day 15	15	[2,21]
	Week 4	28	[22,42]
	Week 8	56	[43,70]

<sup>a Visit name is used to report data in tables, listings and figures.

Week 18     126     [106,147]       Week 24     168     [148 Date of Week 24 Visit]	Week 12	84	[71,105]
Week 24 168 [148 Date of Week 24 Visit]	Week 18	126	[106,147]
110, But 01 (10th 21 115t)	Week 24	168	[148, Date of Week 24 Visit]

When a subject is lost to follow up and last dose date is unknown, impute last dose date of all study drugs as last on-treatment visit date.

<sup>a Visit name is used to report data in tables, listings and figures.

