#### Treatment-emergent (TE) Period

For Part A the TE period will include the time period starting from the first dose date of the study drug to the Follow-up Telephone Call, or the last dose date + 28 days for subjects who do not have a Follow-up Telephone Call. The TE period will be used for safety analyses unless specified otherwise.

For the combined Part B and Part A/B Cohort 8 the TE period will include the time period starting from the first dose date of the study drug to the Follow-up Visit, or to the end of study date for subjects who roll over into the Extension Study and for whom the Follow-up Visit is not required. The last dose date + 28 days will be used as the TE period end date for subjects who do not have a Follow-up Visit or an end of study date. The TE period will be used for safety analyses unless specified otherwise.

**Unscheduled visits:** Unscheduled visit measurements will be included in analysis as follows:

- In scheduled visit windows per specified visit windowing rules (Combined Part B and Part A/B Cohort 8 only).
- In the derivation of baseline measurements.
- In the derivation of maximum/minimum on-treatment values and maximum/minimum change from baseline values for safety analyses.
- In individual subject data listings as appropriate.

**Visit windowing rules:** The analysis visit windows for protocol-defined visits are provided in Appendix D. The windows will be applied using the following rules for both scheduled and unscheduled visits. If no measurement is available within a visit window, the assessment will be considered missing for the visit. If there is more than one measurement available within the same visit window, the following rules will be used:

• For all safety parameters, if there are multiple measurements within a visit window, then 1) the record closest to the target day will be used, with the exception of the threshold analysis in which the worst record will be used; 2) if there are multiple records within the same distance of the target day, the latest record will be used; or 3) the Safety Follow-Up (SFU) visit will not be windowed; instead, the nominal visit will be used in relevant

analyses; 4) the Follow-Up OE visit will not be windowed; instead, the nominal visit will be used in relevant analyses.

- For all efficacy parameters, if there are multiple measurements within a visit window, the record at the scheduled visit will be used. Otherwise,

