#### 8.2.4 Study Drug Exposure

Duration of study drug exposure (in days) will be calculated as: last dose date – first dose date + 1 day, regardless of study drug interruption.

Exposure summaries will be based on the Safety Set.

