## 8.2.5 Study Drug Compliance (Combined Part B and Part A/B Cohort 8 only)

Study drug compliance based on the number of sachets taken will be calculated as:  $100 \times [(\text{total number of sachets dispensed}) - (\text{total number of sachets returned})]/(\text{total number of sachets planned to be taken per day} \times \text{duration of study drug exposure in days}).$  The maximum percentage of sachets taken will be 100%.

Note: For Part A/B Cohort 8 only, multiple sachets of 5.7 mg will be used to achieve doses of 11.4, 17.1, and 22.8 mg. Total number of sachets planned to be taken per day to achieve each dose is:

Doses (q12h) Total number of sachets of planned to be taken per day

5.7mg	2
11.4mg	4
17.1mg	6
22.8mg	8

Study drug compliance based on study drug exposure will be calculated as:  $100 \times [1 - (total number of days of any study drug interruption) / (duration of study drug exposure in days)].$ 

Study drug compliance will be summarized descriptively by the number of subjects (n), mean, SD, SE, median, min, and max. They will also be summarized in categories: <80% and  $\ge80\%$  using frequency tables.

Study drug compliance summaries will be based on the Safety Set.

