#### 8.2.6 Important Protocol Deviations/Violations

Important protocol deviations (IPD) are a subset of protocol deviations that may significantly impact the completeness, accuracy, and/or reliability of key study data or that may significantly affect a subject's rights, safety, or well-being. IPD rules will be developed and finalized before database lock.

The protocol deviations that should be considered as potential IPDs include, but are not limited to:

- Violation of subjects rights, safety or well-being
- Subject entered the study despite violation of any inclusion or exclusion criteria
- Subject was less than 80% compliant with study medications
- Subject received excluded concomitant medications
- Subject received the wrong treatment or incorrect doses
- Subject remained in study despite meeting withdrawal criteria

Occurrence of any of these events should be considered as potential IPDs, but the blinded team should categorize them as IPDs only if they have the potential to affect interpretation of study results.

IPDs will be presented as an individual subject data listing only.

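### For a subject lost to follow-up with an unknown last dose date, sachet compliance counts the unreturned supply from the last visit as taken but leaves out the days it covers, so it is biased upward

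*SAP*

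**What the plan says.** Four provisions of the SAP act together here.

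- **Last dose date.** The notes to the visit-window tables in Appendix D, for both Part B and Part A/B Cohort 8, give this instruction for a subject who is "lost to follow up and last dose date is unknown, impute last dose date of all study drugs as last on-treatment visit date".
- **Exposure.** SAP 8.2.4 defines duration as "last dose date – first dose date + 1 day, regardless of study drug interruption".
- **Sachet compliance.** SAP 8.2.5 takes the "total number of sachets dispensed" minus the "total number of sachets returned" and divides by planned sachets per day times that duration. It then sets a ceiling: "The maximum percentage of sachets taken will be 100" (per cent). Results are also tabulated as <80% and ≥80%.
- **Deviations.** SAP 8.2.6 lists among potential important protocol deviations: "Subject was less than 80% compliant with study medications".

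SAP 8.2.5 also has a second compliance measure, based on days of interruption, which uses no sachet counts.

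The schedules of assessments show drug dispensed in Part B at Day 1 and Weeks 2, 4, 8, 12 and 18, and in Cohort 8 at Day 1, Day 15 and Weeks 4, 8, 12 and 18. Week 24 dispensing is only for subjects entering the Extension Study. Protocol 11.9 has returned sachets counted at visits. Neither document states how many sachets are handed out each time, and the SAP has no rule for sachets that never come back.

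**The concern.** A subject who attends a dispensing visit and is then lost has taken home the supply for the next interval. With the imputed date, the denominator contains none of the days which that supply was meant to cover. The numerator contains all of it, because nothing was returned. The same sachets are in effect treated as not taken for exposure and as fully taken for compliance.

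The error can only run upward, and it falls on the subjects whose adherence is least well known. The cap turns impossible values above 100% into an unremarkable 100%, so the table gives no sign of the problem. It is also a step away from Protocol 13.5.2.4, which defines compliance by dosing occasions given against dosing occasions planned.

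What is at stake is the descriptive compliance summary, the split at 80%, and the use of that cut-off to pick out potential important deviations.

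**Working it through.** **Inputs.**
- L, the study day of the last attended visit. It equals the imputed duration, because first dose is on Day 1 and duration is last dose minus first dose plus 1. Target days 14, 28, 56, 84, 126 and 168 are from SAP Appendix D.
- S, days of supply dispensed at that visit and not returned. This is an assumption: exactly enough to reach the next target visit.
- c, true compliance up to the last visit. The value 50% is an illustration and is not in the documents. Sachets dispensed earlier are assumed to have been returned and counted correctly.

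The plan states no compliance figure, so there is none to reproduce. As a check on the inputs, the planned sachets per day in SAP 8.2.5 for Cohort 8 (2, 4, 6, 8) equal two doses a day times 1, 2, 3 or 4 sachets of 5.7 mg.

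**Formula.** With sachets per day constant, they cancel from SAP 8.2.5:

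raw value = 100 × (c × L + S) / L; shown value = the smaller of 100 and the raw value.

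The upward shift before the cap is 100 × S / L. The lowest true compliance that still shows as 80% or more is 80 − 100 × S / L, or 0 if that is negative.

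**Part B, c = 50%.**

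| Last visit | L | S | 100 × S/L | Raw value | Shown | Lowest true compliance shown as ≥80% |
|---|---|---|---|---|---|---|
| Week 2 | 14 | 14 | 100 | (7 + 14)/14 = 150% | 100% | 0% |
| Week 4 | 28 | 28 | 100 | (14 + 28)/28 = 150% | 100% | 0% |
| Week 8 | 56 | 28 | 50 | (28 + 28)/56 = 100% | 100% | 30% |
| Week 12 | 84 | 42 | 50 | (42 + 42)/84 = 100% | 100% | 30% |
| Week 18 | 126 | 42 | 33.3 | (63 + 42)/126 = 83.3% | 83.3% | 46.7% |

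**Sensitivity.** With five extra days of supply at each dispensing, Weeks 2 to 12 still show 100%, and Week 18 shows (63 + 47)/126 = 87.3%. If the visit falls one day late, Week 8 shows (28 + 28)/57 = 98.2% and Week 12 shows (42 + 42)/85 = 98.8%.

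**Cohort 8, last visit Day 15, unchanged dose.** S = 28 − 15 = 13, so the raw value is (7.5 + 13)/15 = 136.7%, shown as 100%.

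**With the last visit's unreturned sachets removed.** The numerator becomes c × L, and 50% true compliance shows as 50% at all five Part B visits.

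**The case against.** Several points on the other side have force.

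- **The quantity dispensed is unknown.** This stands: the percentages above illustrate one assumption. The direction of the bias does not depend on it, since any unreturned supply raises the numerator only.
- **The cap limits the reported gain.** This also stands. A subject truly at 90% can gain at most 10 points, so a large distortion needs both loss to follow-up and poor adherence.
- **The formula counts unreturned sachets as taken even when the last dose date is known.** True. The imputation is not the only route to the error. It is the route that guarantees the mismatch, because it sets the covered days in the denominator to none.
- **Sachets might still come back.** Protocol 10.4 asks the investigator to request return of unused product. Where that works, the returned sachets are subtracted as they should be.
- **The note sits under visit-window tables.** It is nevertheless the SAP's only rule for an unknown last dose date, and 8.2.4 needs such a date.
- **Little depends on the result.** Compliance is descriptive and defines no analysis set. The 80% item is only a potential deviation for the team to judge, it does not name the sachet measure, and important deviations are only listed. This is why the point is minor.

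A reader might go further and infer that the imputed date also cuts the treatment-emergent period short and drops late adverse events from the tables. The documents do not support that. The fallback of 28 days after last dose in SAP 8.1 applies only when there is neither a Follow-up Visit nor an end of study date, and nothing shows that a lost subject would lack the latter. The harm would also need events learned of later in a subject who is lost, while Protocol 14.1.1.3 ends routine collection for early discontinuers at the ETT or Follow-up Visit. Any such event would still appear in the full listing under SAP 8.4.1.

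**Conclusion.** The point holds, as a minor one. For subjects in Part B or Cohort 8 who are lost with an unknown last dose date, the sachet-based measure uses a numerator and a denominator that cover different days. The bias is upward, and the cap conceals it.

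Assuming Part B supply exactly to the next visit, true compliance of 50% is shown as 100% after loss at Weeks 2 to 12 and as about 83% after loss at Week 18. It would be wrong to read this as 100% whenever true compliance is 50%, because Week 18 does not reach that figure. Nor does it mean that poor adherence escapes notice altogether: sites count returns at visits, and the interruption-based measure is untouched, although that measure uses no sachet count and so cannot correct the sachet table.

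Few subjects should be affected, but SAP 8.1 presents tables by cohort. At the Part B minimum of five subjects, one subject shown as 100% instead of 50% moves the cohort mean by 50/5 = 10 points. Larger cohorts dilute this, and Part B has no stated maximum.

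**What to change.** Add one sentence to SAP 8.2.5: when the last dose date has been imputed as the last on-treatment visit, sachets dispensed on or after that date and not returned are excluded from the numerator. Numerator and denominator then cover the same days. The imputation itself, the exposure definition and the treatment-emergent period stay as they are.

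The sentence does not reach a Cohort 8 subject whose last visit is Day 4. Nothing is dispensed or counted at that visit, and the outstanding supply is from Day 1. At two sachets a day and 14 days of supply, the formula gives 28/8 = 350%, shown as 100% whatever was taken. Reporting sachet compliance as missing in that case would close the gap.

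The cost is a line or two of text and a small programming change. No new data are needed. The downside is slightly lower reported compliance for the few subjects affected.
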